**Changes in corneal endothelial cell density
after transscleral ab interno glaucoma gel stent implantation**

STUDY SPONSOR:

Dept. Ophthalmology and Optometry, Paracelsus Medical University Salzburg
[name]
[name]
Austria

NCT04547036

PROTOCOL DATE:

October 15th, 2018

REV. A

Please Note: Confidential information contained herein is made available to you in your capacity as Investigator, Medical Advisor, or Consultant. It is provided only for review by you, your staff, Ethics Committee members, or other regulatory authority. Except as necessary to obtain properly informed consent for participation, it is expected that there will be no disclosure to other persons.

Investigator Statement of Compliance

As an Investigator, I agree to: 1) Implement and conduct this study diligently and in strict compliance with this protocol, applicable government laws and regulations, conditions of approval imposed by the reviewing ethics committee or competent authority, the Declaration of Helsinki and Good Clinical Practice / ICH Guidelines. 2) Supervise all testing of the device involving human subjects, 3) Ensure that the requirements for obtaining informed consent are met and 4) Maintain all information supplied by the Sponsor in confidence and, when this information is submitted to an EC or any other group, it will be submitted with a designation that the material is confidential.

Investigator Signature

Date

REVISION HISTORY

Date	Revision
October 15th, 2018	A

Protocol Outline

Protocol Title: "Changes in corneal endothelial cell density after transscleral ab interno glaucoma gel stent implantation"

Protocol Version: A

Protocol Date: October 15st 2018

Principal Investigator: [name]. [name]

Research Team: [name]. [name], Doz. Dr. [name], Dr. [name]

I. Abstract

STUDY OBJECTIVE	Corneal endothelial cell loss is a known sequela of glaucoma tube shunt implantation. Big tube shunts show a decrease of endothelial cell count postoperatively (-11.5% after Ahmed glaucoma valves and -12.4% after Molteno shunt 2 years postoperatively). The objective of this study is to evaluate the change of endothelial cell count after XEN45 in patients with or without cataract operation.
PATIENT POPULATION	In 140 open angle eyes central endothelial cell counts were recorded preoperatively, before the XEN45 implantation was performed in Dept. Ophthalmology at Paracelsus Medical University Salzburg. XEN45s were already performed in the year 2013-2017 (so up to 5 years) in open angle glaucoma eyes in combination with or without cataract operation. In these eyes central endothelial cell count and central corneal thickness was measured preoperatively and documented in patients records.
STUDY DESIGN	A prospective, observational, monocentric trial to evaluate the course of endothelial cell density after the XEN implant. The study will take place in the Dept. Ophthalmology at Paracelsus Medical University Salzburg/SALK.

Up to 140 consecutive patients with preoperatively recorded endothelial cell counts will be summoned to a consecutive endothelial cell count record and measurement of central corneal thickness

postoperatively. Informed consents will be obtained from patients, who are interested in participating in the study.

Patients will be assessed for endothelial cell density and the position of the XEN45 measured by anterior segment optical coherence tomography. The distance of the XEN45 to cornea, the angle of the tube, and the tube length in the anterior chamber will be recorded with anterior segment optical coherence tomography. Endothelial cell density will be measured on 3 positions: central, superior-nasal (location of XEN45 implantation), infero-temporal (far away for the XEN45 implant).

OUTCOME PARAMETERS	
The primary endpoint is the change of central endothelial cell density compared to preoperative data.
 
Secondary objectives are the differences of supero-nasal and infero-temporal endothelial cell density compared to the central endothelial cell density, and pachymetry compared to preoperative data.

EXAMINATION SCHEDULE	Subjects will undergo study visits at the following times: preoperative data (2013-2017) out of patient records, postoperative visit in the year 2018-2019 (1-6 years post XEN45 implantation).
CLINICAL PARAMETERS	
The following clinical assessments will be performed at the postoperative examination:
 
1. Endothelial cell count on different locations of the study eye2. Central corneal thickness3. Anterior segment optical coherence tomography (to determine the position of the XEN45)4. Slit lamp examination of the cornea, anterior segment including gonioscopy (to determine the position of the XEN45), and dilated fundus examination5. Best corrected visual acuity6. Measurement of IOP7. Number and frequency of ocular (glaucoma) medications8. Ocular symptoms and assessment of complications (especially symptoms, which may be a hint for loss of endothelial cell count)

9. Secondary surgical procedures (if applicable including needlings, lasers, cataract operation, bleb revisions, keratoplasty, secondary IOP lowering procedures, other operations)

II. Background and Significance/Preliminary Studies

Glaucoma is a leading cause for irreversible visual function loss worldwide.¹ However, the reduction of intraocular pressure (IOP) is the only proven therapy for glaucoma. To reduce the IOP, most patients are treated with IOP lowering eye drops, but there is a rising group of patients, which has an unmet need for surgical IOP reduction.²⁻⁶ All members of the commonly performed filtering glaucoma surgeries (e.g. trabeculectomy or big tube shunts) are capable to lower the IOP.

In the last years, new minimally invasive glaucoma surgeries (MIGS), have been introduced for glaucoma therapy.⁷⁻⁹ The XEN Glaucoma Gel Microstent (XEN-GGM, Allergan Plc, USA) is a member in the MIGS group.¹⁰ It bypasses aqueous humor from the anterior chamber to the subconjunctival space.¹¹

Corneal endothelial cell loss is a known sequela of glaucoma tube shunt implantation.¹² Big tube shunts show a decrease of endothelial cell count postoperatively (-11.5% after Ahmed glaucoma valves and -12.4% after Molteno shunt 2 years postoperatively).¹³⁻¹⁵ Corneal endothelial cell density further progressively decreased after Ahmed glaucoma valve implantation with time. The distance of the Ahmed tube tip to the cornea is significantly associated with endothelial cell loss in the quadrant of implantation.¹³⁻¹⁵ A dramatic decrease of endothelial cells may cause corneal edema and affects the patient's vision. Even a keratoplasty (transplantation of the cornea or the corneas' inner layers) may be necessary due to a massive decrease of endothelial cell density.

Also after classic filtering surgery (trabeculectomy with and without Mitomycin C), a significant loss of endothelial cells is reported.¹⁶

The Cypass Implant (Alcon), a minimally invasive glaucoma surgery (MIGS) competitor to the XEN45, was withdrawn from global market due to statistically significant endothelial cell loss at 5 years. (see <https://www.alcon.com/news/media-releases/alcon-announces-voluntary-global-market-withdrawal-cypass-micro-stent-surgical>)

Therefore the objective of this study is to evaluate the change of endothelial cell count after XEN45 in combination with or without cataract operation.

III. Study Aims

The present study aims to longitudinally evaluate the change of endothelial cell count after XEN45 in 2 patient groups: XEN solo procedures and combined XEN with cataract operations.

IV. Administrative Organization

In 140 open angle eyes preoperative central endothelial cell counts were recorded preoperatively, before the XEN45 implantation was performed. XEN45s were already performed in the year 2013-2017 (so up to 5 years) in open angle glaucoma eyes in combination with or without cataract operation. In these eyes central endothelial cell count and central corneal thickness was measured preoperatively and documented in patients records.

The study will take place in the Dept. Ophthalmology at Paracelsus Medical University Salzburg/SALK.

V. Study Design

Experimental design of the study

A prospective, observational, monocentric trial to evaluate the course of endothelial cell density after the XEN implant.

Up to 140 consecutive patients with preoperatively recorded endothelial cell counts will be summoned to a consecutive endothelial cell count record and measurement of central corneal thickness postoperatively. Informed consents will be obtained from the patients, who are interested in participating in the study. The study will be approved by the local ethics committee.

Patients will be assessed for endothelial cell density and the position of the XEN45 measured by anterior segment optical coherence tomography. The distance of the XEN45 to cornea, the angle of the tube, and the tube length in the anterior chamber will be recorded with anterior segment optical coherence tomography. Endothelial cell density will be measured on 3 positions: central, superior-nasal (location of XEN45 implantation), infero-temporal (far away for the XEN45 implant).

Subjects will undergo study visits at the following times: preoperative data (2013-2017) out of patient records, postoperative Visit in the year 2018-2019 (1-6 years post XEN45 implantation).

2 patient groups will be analyzed separately: patients, who had a solo XEN procedure and patients, who had a combined XEN and cataract operation.

Study population general description

This study will include subjects presenting with open angle glaucoma and who meet the following inclusion and exclusion criteria. Any questions regarding a patient's eligibility should be discussed with the sponsor prior to enrollment.

An inclusion of both eyes of the same patient is possible.

Inclusion Criteria

1. Open Angle Glaucoma
2. History past XEN45 implantation with or without combined cataract procedure
3. Available preoperative endothelial cell count data not older than 1 year before XEN operation without any operation between the day of data record and XEN45 operation.
4. Age 18 years or older and of legal age of consent
5. Signed written informed consent
6. Availability, willingness, and sufficient cognitive awareness to comply with examination procedures

Exclusion Criteria

1. Patients with secondary IOP lowering procedures (excluding SLT, needlings, bleb revisions, YAG lasers, Argon lasers) after XEN implantation will be excluded from analysis, because the secondary IOP lowering procedures may influence endothelial cell count itself. Cataract operations without complications are no exclusion criteria, but have to be recorded.

Sample size determination and power analysis

No formal sample size calculation was done due to the unknown effect size.

Description of hypothesis for primary endpoint:

Null hypothesis: H0: the postoperative mean number of endothelial cells is lower than the preoperative.

Alternative hypothesis: H1: the postoperative mean number of endothelial is larger or equal than the preoperative

Study outcomes/endpoints

The primary endpoint is the change of central endothelial cell density compared to preoperative data.

Secondary objectives are the changes of supero-nasal and infero-temporal endothelial cell density compared to the central endothelial cell density, and pachymetry compared to preoperative data.

VI. Study Procedures

Slit lamp examination

The visibility of the XEN in slit lamp examination in eyes looking directly to the examiner will be recorded (yes/no). Beside biomicroscopic slit lamp examination of the cornea and anterior segment, signs of inflammation or corneal alterations will be recorded.

Gonioscopy

Gonioscopy and angle assessment of XEN quadrant (superior-nasal) by Shaffer Grade. The position of the XEN will be noted (anterior Schwalbe line = in cornea, in Schwalbe line, anterior to Schlemm's Canal, in Schlemm's Canal, non pigmented Trabecular meshwork, pigmented Trabecular meshwork, posterior pigmented trabecular meshwork, scleral Spur, ciliary body band, Iris), the length of the XEN stent in anterior chamber will be noted, if there is an endothelial/iris touch of the XEN stent will be noted:

FIGURE 1: Shaffer Angle Grading

[figure not shown]

TABLE 1: SHAFFER GRADE FOR ANGLE EVALUATION

Shaffer Grade	Angle
Grade 4	45-35° angle
Grade 3	35-20° angle
Grade 2	20° angle
Grade 1	10° angle or less
Grade 0	0° angle (closed)

Optical coherence tomography

Anterior segment optical coherence tomography (AS-OCT) is used to determine the position of the XEN45 in the anterior chamber. The distance of the XEN45 to cornea, the angle of the tube, and the tube length in the anterior chamber will be recorded with anterior segment optical coherence tomography.

Endothelial cell count

Endothelial cell density will be measured on 3 positions: central, superior-nasal (location of XEN45 implantation), infero-temporal (far away for the XEN45 implant).

Pachymetry

The central corneal thickness has to be measured in the cornea center.

Dilated fundus examination

Per clinical routine.

Measurement of IOP

[figure not shown]
Goldmann applanation tonometry are used to measure IOP. IOP readings are repeated until 2 consecutive or nonconsecutive measurements are obtained differing by 1 mmHg or less, and the average of the 2 readings serves as the IOP measurement for the visit.

Best corrected visual acuity

Before BCVA testing, the investigator performs a manifest refraction. Once the best-corrected manifest refraction was determined, best corrected visual acuity on the study eye was examined with the patients' pupils in their natural state. The pinhole method for measuring visual acuity is not acceptable.

The BCVA has to be tested at a single seating by the same experienced investigator in the same room from a 4 meters distance with standardized low light conditions. A comfortable seating of the patient and to the chart placement at eye level is important while testing visual acuity. The patients have to be told not to lean forward. Breaks during the testing are allowed as needed.¹⁷
¹⁸

FIGURE 2: ETDRS chars

The ETDRS logMAR charts (Lighthouse International, New York, NY) are used for assessment of best corrected distance visual acuity. The chart has five letters per row ranging in size from +1.0 to -0.30 logMAR at 4 meters.

Testing Paradigm for distance BCVA. Subjects are required to identify each letter on the chart until they identified a full row of letters incorrectly, at which point the test was terminated, and the acuity calculated. Vision testing starts with the top of the chart. Patients are elated to guess if they were not sure of the letter. Only a single reading of the chart is allowed. When a letter is read correctly, the examiner circles this letter on a score sheet with a layout identical to that of the chart. If visual acuity is poor, the test distance is reduced to 1 meter. Visual acuity as low as 0,025dec (+1,6logMAR) can be measured.

If patients could not see any letter of EDTRS chart at 1 meter, they are tested for finger count (0,01dec, logMAR +2), hand movement (0,001dec, logMAR +3) or light perception visual acuity (0,0001dec, logMAR +4) at 0.6 meters.¹⁹ Results are recorded on a sheet.

Scoring Snellen for distance BCVA. Snellen line assignment method is used to score results. The smallest line, where a patient has read half or more of the letters correctly, is recorded as BCVA in Snellen (decimal).

Ocular symptoms and assessment of complications

Especially symptoms, which may be a hint for loss of endothelial cell count have to be recorded.

Secondary surgical procedures

If applicable record secondary surgical procedures including needlings, lasers, cataract operation, bleb revisions, keratoplasty, secondary IOP lowering procedures, other operations.

VII. Visit

Subjects will be examined and evaluated according to the following schedule of visit:

Visit	Exam	Visit Window
Preop	preoperative data out of patient chart records	(2013-2017)
PO1	Visit	Year 2018-2019 (1-6 years post XEN45 implantation).

Preoperative Procedures

No subject may be entered into the study who does not meet the inclusion/exclusion criteria. The details of the study must be fully explained and informed consent must be signed prior to any study-specific examinations being performed.

Visit

The visit will request the following information:

Exams	Screening Evaluation
Informed Consent	Yes
Demographic Information	Yes
Ocular History and Medications	Ocular history, including presence of ocular pathology and ocular medications
Glaucoma History and Medications	Including number of IOP Lowering Medications
Secondary surgical procedures	if applicable including needlings, lasers, cataract operation, bleb revisions, keratoplasty, secondary IOP lowering procedures, other operations
Slit Lamp Exam	Biomicroscopic slit lamp examination of the cornea and anterior segment
Endothelial cell count	Endothelial cell density will be measured on 3 positions: central, superior-nasal (location of XEN45 implantation), infero-temporal (far away for the XEN45 implant).
Pachymetry	Will be measured in the cornea center
Anterior segment optical coherence tomography	to determine the position of the XEN45

Anterior segment optical coherence tomography	Best Corrected distance Visual Acuity (BCVA line assignment method): Monocular best-corrected visual acuity should be measured in Snellen line assignment method.
IOP (Medicated)	Intraocular pressure (IOP) using Goldmann
Gonioscopy	to determine the position of the XEN45
Assessment of Adverse Events and Serious Adverse Events	See Section Adverse Event and Serious Adverse Event Reporting

Safety Monitoring Plan

Definition of adverse events, serious adverse events:

The XEN procedure is standard of care. The XEN implant is CE-marked for the implantation in primary open angle glaucoma patients. XEN is used in the treatment of glaucoma worldwide. Complications occurring during the study period will be treated in the discretion of the treating investigator. In every serious adverse event, appropriate measures should be taken to treat/resolve and monitor the subject. Any subjects who are withdrawn from the study due to an adverse event shall still be followed until the outcome is resolved.

Before and after the study visit, patients will be followed up in the clinical routine.

The investigators will classify the adverse events based on the following definitions according to ISO 14155 (2011).

Adverse Event (AE)

Any untoward medical occurrence, unintended disease or injury, or untoward clinical signs (including abnormal laboratory findings) in subjects, users or other persons, whether or not related to the investigational medical device.

Adverse Device Effect (ADE)

An adverse event related to the use of an investigational medical device.

Device deficiency

Inadequacy of a medical device with respect to its identity, quality, durability, reliability, safety or performance. Device deficiencies include malfunctions, use errors, and inadequate labelling.

Serious Adverse Event (SAE)

An adverse event that a) led to death,
 b) led to serious deterioration in the health of the subject, that either resulted in
 1) a life-threatening illness or injury, or

- 2) a permanent impairment of a body structure or a body function, or
- 3) in-patient or prolonged hospitalization, or
- 4) medical or surgical intervention to prevent life-threatening illness or injury or permanent impairment to a body structure or a body function,

c) led to foetal distress, foetal death or a congenital abnormality or birth defect

NOTE: Planned hospitalization for a pre-existing condition, or a procedure required by the CIP, without serious deterioration in health, is not considered a serious adverse event.

Serious Adverse Device Effect (SADE)

Adverse device effect that has resulted in any of the consequences characteristic of a serious adverse event

VIII. Analysis Plan

Statistical methods

Data consistency was checked and data were screened for outliers and normal, Gamma, Log-normal and Tweedie distributions by using quantile plots. Continuous variables were also tested for these distributions by using Kolmogorov-Smirnov test. Depending on data distribution the following methods will be used: In case of parametrically testing, mixed models based on normal, Gamma and Tweedie distributions will be used to analyze data. Independent and unstructured working correlation matrices were used for modeling the corresponding covariance of Endothelial cell number over time. The model based estimator was used to estimate the covariance matrix. The corrected quasi likelihood under independence of model criterion will be used to select the final models. 95% confidence intervals will be computed for means and results will be illustrated by using Whisker plots. In case of nonparametrically testing, Wilcoxon's matched pairs test will be used. All reported tests will be done one-sided, and p-values < 0.05 were considered as statistically significant. All statistical analyses will be performed by use of STATISTICA 13 (Hill, T. & Lewicki, P. Statistics: Methods and Applications. StatSoft, Tulsa, OK) and NCSS 10 Statistical Software (2015). NCSS, LLC. Kaysville, Utah, USA.

IX. Literature Cited

2. Cairns JE. Trabeculectomy. Preliminary report of a new method. *Am J Ophthalmol* 1968;66:673-9.
5. Leske MC. The epidemiology of open-angle glaucoma: a review. *Am J Epidemiol* 1983;118:166-91.

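### Both eyes of a patient may enter, but the analysis plan does not cluster by patient; its stated variance method can make the standard error of the change too small or too large, depending on which listed option is used.

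*Combined protocol and SAP*

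**What the plan says.** V. Study Design (Study population general description) states: "An inclusion of both eyes of the same patient is possible". It sets no cap and no rule for choosing an eye. IV. Administrative Organization counts the available baselines by eye: "In 140 open angle eyes preoperative central endothelial cell counts were recorded preoperatively". The same section and V. Study Design plan to recall as many as 140 patients, so the ratio of eyes to patients is not fixed.

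V. Study Design has two groups analysed separately, described as "patients, who had a solo XEN procedure and patients, who had a combined XEN and cataract operation". III. Study Aims describes the same groups by procedure. The primary endpoint is the change in central endothelial cell density from the preoperative value.

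VIII. Analysis Plan (Statistical methods) says that on the parametric route "mixed models based on normal, Gamma and Tweedie distributions will be used to analyze data". On correlation it says: "Independent and unstructured working correlation matrices were used for modeling the corresponding covariance of Endothelial cell number over time". On variance: "The model based estimator was used to estimate the covariance matrix". On selection: "The corrected quasi likelihood under independence of model criterion will be used to select the final models". The nonparametric route is Wilcoxon's matched pairs test. Tests are one-sided at 0.05, and means carry 95% confidence intervals. The section names no random effect, subject or cluster identifier, robust variance, averaging of the two eyes or one-eye rule.

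**The concern.** Fellow eyes share a patient's age, systemic health and often surgeon and technique, so their changes in cell density may well be positively correlated. An analysis that treats such eyes as independent claims more information than it has: intervals are too narrow and the one-sided level exceeds 5%, on whichever side the test is run.

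The plan allows bilateral inclusion and then lists methods that, followed as written, do not allow for it. One of the listed options also ignores the pairing of each eye's pre- and postoperative values, which pushes the error the other way. No sample size calculation was done, so the study's message rests on the interval and p-value for the mean change. Both depend on a standard error that the plan leaves open.

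**Working it through.** The plan states no SD, power or sample size calculation, so there is no figure of its own to reproduce.

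**Inputs from the protocol:** 140 eyes with a baseline; two groups analysed separately; one-sided alpha 0.05; 95% intervals.

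**Assumed inputs (not in the documents):** f, rho (both as the share and correlation within one group) and r, the pre/post correlation within an eye. If f applied to all 140 eyes, the number of patients would be 140·(1 − f/2): 133 at f = 0.1 and 126 at f = 0.2.

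**Step 1: pairing by eye kept, patient ignored.** For E eyes in a group, with fE/2 bilateral patients and SD of change s:

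Var(mean change) = (1/E²)·[E·s² + 2·(fE/2)·rho·s²] = (s²/E)·(1 + f·rho).

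The eye-level analysis reports s²/E. So true SE / reported SE = sqrt(1 + f·rho), one-sided level = 1 − Phi(1.645/sqrt(1 + f·rho)), and coverage = 2·Phi(1.96/sqrt(1 + f·rho)) − 1.

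| f | rho | 1 + f·rho | SE ratio | one-sided level | coverage |
|---|---|---|---|---|---|
| 0 | any | 1.00 | 1.000 | 5.0% | 95.0% |
| 0.1 | 0.2 | 1.02 | 1.010 | 5.2% | 94.8% |
| 0.1 | 0.5 | 1.05 | 1.025 | 5.4% | 94.4% |
| 0.1 | 0.8 | 1.08 | 1.039 | 5.7% | 94.1% |
| 0.2 | 0.2 | 1.04 | 1.020 | 5.3% | 94.5% |
| 0.2 | 0.5 | 1.10 | 1.049 | 5.8% | 93.8% |
| 0.2 | 0.8 | 1.16 | 1.077 | 6.3% | 93.1% |

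**Step 2: which methods this covers.** It covers the unstructured matrix with the eye as subject, and the Wilcoxon test. It also covers an identity-link mixed model with random intercepts only. In that model, post minus pre equals the visit effect plus a difference of residuals, so patient and eye intercepts drop out and the SE stays at its eye-paired value. In 24 fitted data sets, the SE of the visit effect with patient and eye intercepts was 1.00 times the eye-paired SE in 22 and 0.99 in 2. The cancellation is not shown for a Gamma or Tweedie model with another link.

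**Step 3: simulation.** One group of 70 eyes (140 split equally, assumed), 7 bilateral patients (f = 0.2), rho = 0.5, r = 0.7, assumed mean 2200 and SD 300, no true change, 20,000 runs. Where two levels are given, they are for the lower and upper one-sided tests.

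- Eye-paired analysis: reported SE 27.6 against a true 29.1; level 5.9/6.0%; coverage 93.9%.
- Plain Wilcoxon: level 5.9/5.9%.
- Patient-clustered sandwich variance: level 5.2/5.1%; coverage 94.9%.
- Cluster-adjusted signed-rank test: level 5.1%.
- One eye per patient: level 5.1/5.0%.

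**Step 4: independent matrix with model-based errors.** With SD the common SD of a single measurement, the true variance is 2·SD²·(1 − r)·(1 + f·rho)/E, and the reported variance is 2·SD²/E. Reported SE / true SE = 1/sqrt((1 − r)(1 + f·rho)).

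- Before clustering (f = 0): 1/sqrt(1 − r) = 1.41 at r = 0.5 and 1.83 at r = 0.7.
- At f = 0.2, rho = 0.5: 1/sqrt(0.5 × 1.10) = 1.35 and 1/sqrt(0.3 × 1.10) = 1.74. The one-sided level is then about 1.3% and 0.2%.
- Break-even is r = f·rho/(1 + f·rho): 0.10/1.10 = 0.09 at f = 0.2, rho = 0.5, and 0.16/1.16 = 0.14 at f = 0.2, rho = 0.8. Above that the SE is too large.

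**Step 5: the selection criterion.** The plan says only that it selects the final models. If it is used to choose the correlation structure, it gives no protection. The criterion is −2Q + 2p with Q computed under independence, and for a given mean model the independence fit maximises Q, so the unstructured fit can only tie or score worse.

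**The case against.** The plan does not say that eyes will be treated as independent. It does not say what the subject is, and a patient-level block with an unstructured matrix could take in fellow eyes. That is fair, but the only correlation described is over time, and nothing shows that a patient block was intended. The Wilcoxon fallback has no such room.

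The size may be nil. As many as 140 patients for 140 eyes is compatible with few or no bilateral patients, and because the groups are analysed separately only fellow eyes in the same group matter. This stands in full. At f = 0.1 the loss is slight.

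Three stronger readings are tempting and should not be drawn:

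- **That the standard error is understated whatever is done.** Step 4 shows that the independent matrix with model-based errors goes the other way for any but a low pre/post correlation.
- **That the level is doubled.** If every eye came from a bilateral patient within its group (f = 1, rho = 0.8), the level would be 11.0% and coverage 85.6%. Nothing in the documents supports that share.
- **That a patient with one solo and one combined eye has no group.** Study Aims groups by procedure, so assignment by that eye's operation is the natural reading. The patient-based wording in Study Design needs only a clarifying phrase.

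**Conclusion.** The concern holds in limited form. Bilateral inclusion is allowed, and the variance methods listed do not provide for it. That much is plain from the text.

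The consequence depends on choices and quantities that the documents leave open. With pairing by eye kept and a positive between-eye correlation of change, the SE is too small by 1 to 8% of its reported value over the assumed range (ratio 1.010 to 1.077), and there is no effect without bilateral patients in a group. With the independent matrix and model-based errors, the SE is too large, by 35% at f = 0.2, rho = 0.5, r = 0.5.

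The stated method can therefore be wrong in either direction. This should be corrected before analysis because the correction is cheap. For modest bilateral shares it is not a threat to the study's main conclusion.

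**What to change.** In VIII. Analysis Plan, Statistical methods:

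1. Add: *The eye is the unit of analysis, assigned to the solo or combined group by the procedure done in that eye. The patient is the cluster.*
2. Replace "The model based estimator was used to estimate the covariance matrix" with: *Standard errors use a robust (sandwich) variance clustered on patient, with t limits on the number of patients minus 1 degrees of freedom.* This also removes the problem in step 4, since the sandwich variance does not rely on the working matrix being right.
3. Replace the plain Wilcoxon test with a cluster-adjusted signed-rank test: sum the signed ranks within each patient, then divide the total by the root of the sum of squared patient sums. Alternatively, use one eye per patient, chosen by a pre-stated rule.
4. Report eyes, patients and bilateral patients in each group.

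No new data or visits are needed. Against a naive eye-level analysis, intervals widen by about 2% at f = 0.1 and 5% at f = 0.2 (rho = 0.5: sqrt(1.05) = 1.025, sqrt(1.10) = 1.049). The one-eye rule would drop f/2 of the eyes: 5% at f = 0.1 and 10% at f = 0.2. Whether the two named packages fit these methods was not checked, so another package may have to be named.

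### The primary hypotheses put cell loss in the null and, with one-sided testing and no margin, leave a primary test that can reach significance only on an observed rise in cell density

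*Combined protocol and SAP*

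**What the plan says.** Section V (Study Design), under the description of the hypothesis for the primary endpoint, gives two lines: "Null hypothesis: H0: the postoperative mean number of endothelial cells is lower than the preoperative" and "Alternative hypothesis: H1: the postoperative mean number of endothelial is larger or equal than the preoperative". Neither includes a margin or an acceptable loss, and none is given elsewhere. The same section says that no formal sample size calculation was done.

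Section VIII (Analysis Plan, Statistical methods) adds: "All reported tests will be done one-sided, and p-values < 0.05 were considered as statistically significant". It names no direction, so the direction can come only from the two lines in section V. The rule covers the mixed-model route and also the nonparametric route, where Wilcoxon's "matched pairs test will be used". Section VIII also says that "95% confidence intervals will be computed for means".

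Section II explains why the study is done. It cites endothelial losses of 11.5% and 12.4% two years after larger tube shunts, and the market withdrawal of a competing device because of cell loss. It then concludes: "Therefore the objective of this study is to evaluate the change of endothelial cell count after XEN45".

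**The concern.** A one-sided test can support only its alternative. Here the alternative is no loss or a gain, while the background is concerned with loss. If the plan is followed literally, a real loss gives a p-value near 1 and is labelled not significant. An implant with no effect on the endothelium is also labelled not significant 95% of the time. Both situations would usually be reported in the same way, and failing to reject this null is not evidence of loss.

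The p-value can also contradict the study's own confidence interval. An analyst who notices this may reverse the direction at analysis, and the primary conclusion would then rest on a choice that the plan does not record.

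**Working it through.** The plan gives no power or sample size figure to reproduce, so the check evaluates the test as worded.

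**Inputs from the documents.** Null: mean change (postoperative minus preoperative) below 0. Alternative: mean change at or above 0. One-sided alpha 0.05. At most 140 eyes with preoperative counts (section IV), with solo and combined procedures analysed separately (section V). Reference loss 11.5% (section II, Ahmed valve).

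**Assumptions, not in the documents.** SD of the change 10% to 20% of baseline, with 25% as a sensitivity value; 35, 70 or 140 independent eyes per test; a paired t-test as a simple stand-in for the planned models.

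**Rejection rule.** Reject if d / (SD/√n) > t(0.95, n−1), where d is the observed mean change. The right-hand side is positive, so d must be positive. The smallest observed rise that is significant is t(0.95, n−1) × SD/√n:

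- n = 140, SD 10%: 1.656 × 0.845 = 1.4%
- n = 70, SD 15%: 1.667 × 1.793 = 3.0%
- n = 35, SD 20%: 1.691 × 3.381 = 5.7%

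**Probability that the written test rejects** (noncentral t, noncentrality = true change / (SD/√n)):

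| True change | n = 140, SD 10% | n = 70, SD 15% | n = 35, SD 20% | n = 35, SD 25% |
|---|---|---|---|---|
| 0 | 0.050 | 0.050 | 0.050 | 0.050 |
| −5% | 2.5 × 10⁻¹⁴ | 5.2 × 10⁻⁶ | 0.0010 | 0.0025 |
| −11.5% | about 0 | about 0 | 3.2 × 10⁻⁷ | 8.0 × 10⁻⁶ |

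For 80% power the written test needs a true gain of 2.1% (n = 140, SD 10%), 4.5% (n = 70, SD 15%) or 8.6% (n = 35, SD 20%).

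The Wilcoxon route behaves in the same way. In simulation it rejects with probability 0.0010 and 0.0027 for a true 5% loss at n = 35 with SD 20% and 25%, and about 0.05 at zero change.

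**Conflict with the interval.** Take an observed change of −5% with n = 70 and SD 15%.

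- SE = 15/√70 = 1.793; t = −5/1.793 = −2.789 on 69 degrees of freedom
- 95% CI = −5 ± 1.995 × 1.793 = −8.6% to −1.4%, which excludes zero
- p = 0.997 for the written test, 0.003 with the direction swapped, 0.007 two-sided

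**Power after repair:**

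| True loss, n, SD | Two-sided 0.05 | Swapped, one-sided 0.05 |
|---|---|---|
| 11.5%, 35, 20% | 0.91 | 0.95 |
| 11.5%, 35, 25% | 0.75 | 0.85 |
| 5%, 70, 15% | 0.79 | 0.87 |

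**Fellow eyes.** Section V states "An inclusion of both eyes of the same patient is possible", so independence is optimistic. As a rough bound, suppose every eye has an included fellow eye with correlation 0.5 (also assumed). The design effect is then 1 + 0.5 = 1.5. At n = 35, by normal approximation, two-sided power for an 11.5% loss falls to about 0.79 (SD 20%) or 0.60 (SD 25%). The written test still rejects only 0.0022 or 0.0045 of the time for a 5% loss.

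**The case against.** The strongest reply is that the labels were simply exchanged. The line called H1 contains the equality, which normally belongs in a null. Swapping the labels gives an ordinary one-sided test for loss that fits the background, and a sensible analyst would run that test. This is plausible, and it is why a swap is an acceptable repair. It does not rescue the text, because a second intention fits equally well: a safety layout in which loss is the null and preservation is to be shown. That layout needs a margin, and none is given. The two readings lead to different tests and different conclusions, so the choice has to be written down before the data are seen.

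It can also be said that this is a single-centre observational study whose objective is to evaluate change and which plans confidence intervals. That stands in part: the data, the endpoint and the estimates are unaffected, and an interval could show a loss. But these are the only hypotheses stated for the primary endpoint and a significance threshold is attached to them, so a p-value will be reported. The interval wording also refers only to means and leaves open whether the mean change receives one.

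Two technical limits are fair. The figures use a paired t-test, whereas the parametric plan is mixed models with normal, Gamma or Tweedie distributions, so the very small probabilities show order of magnitude only. And what is required is an observed rise, not a true one; for Wilcoxon it is a predominance of increases in the signed ranks. Neither changes the direction of rejection.

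**Conclusion.** The concern holds and must be fixed. Under either reading of the authors' intention, the written primary test cannot demonstrate loss and cannot credibly demonstrate its absence. That conclusion follows from the wording alone.

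The size depends on the assumed SD and number of eyes. Over SD 10% to 20% and 35 to 140 independent eyes, the written test rejects at most 0.1% of the time under a true 5% loss (0.25% at n = 35, SD 25%). A correctly directed or two-sided test would have power of at least 0.91 for an 11.5% loss (at least 0.75 at SD 25%). The defect is confined to the hypothesis test.

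A lesser, separate point is that the one-sided rule also covers the secondary comparisons, for which no direction is stated: "Secondary objectives are the changes of supero-nasal and infero-temporal endothelial cell density compared to the central endothelial cell density", together with pachymetry. If the direction of such a test were chosen after seeing the data, its false-positive rate would be about 0.05 + 0.05 = 0.10.

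**What to change.** In section V, replace both hypothesis lines with: *H0: the mean change in central endothelial cell density (postoperative minus preoperative) equals 0. H1: the mean change differs from 0. Two-sided alpha 0.05.* This suits an objective stated without direction. The smallest acceptable repair is to swap the directions: *H0: mean change ≥ 0 (no loss). H1: mean change < 0 (loss). One-sided alpha 0.05.*

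In section VIII, add: *The primary result in each group is the mean change, absolute and percent, with its two-sided 95% confidence interval.* For the secondary comparisons, use two-sided tests or state each direction in advance. Any claim of no relevant loss should compare the lower confidence limit of the change with a margin that the sponsor specifies and justifies beforehand; a non-significant p-value is not enough.

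The cost is wording in two sections, with no added patients or measurements. The two-sided test gives up some power against the swapped one-sided test (0.79 versus 0.87 for a 5% loss at n = 70, SD 15%). Against the written test, no ability to detect loss is given up.
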